6.8.2.1 Risk minimisation activities for risks associated with sunitinib

Adrenal function: Physicians prescribing SUTENT are advised to monitor for adrenal insufficiency in patients who experience stress such as surgery, trauma or severe infection.

Dermatologic: Severe cutaneous reactions have been reported with sunitinib, including cases of erythema multiforme (EM), Stevens-Johnson syndrome (SJS), and toxic epidermal necrolysis (TEN), some of which were fatal. If signs or symptoms of SJS, TEN, or EM (eg, progressive skin rash often with blisters or mucosal lesions) are present, sunitinib should be discontinued. If a diagnosis of SJS or TEN is suspected, sunitinib must not be re-started.

Hepatic: Sunitinib has been associated with hepatotoxicity, which may result in liver failure or death. Liver failure has been observed in clinical trials (7/2281 [0.3%]) and post-marketing experience. Liver failure signs include jaundice, elevated transaminases and/or hyperbilirubinemia in conjunction with encephalopathy, coagulopathy, and/or renal failure. Sunitinib should be interrupted for Grade 3 or 4 drug-related hepatic adverse events and discontinued if there is no resolution. Do not restart sunitinib if patients subsequently experience severe changes in liver function tests or have other signs and symptoms of liver failure.

Hypertension: Patients should be monitored for hypertension and treated as needed with standard anti-hypertensive therapy. Interruption and re-initiation at a reduced dose should be implemented as per Table 8. Grade 3 hypertension ($>160/100$, more intensive therapy than was previously used indicated) was observed in 50/375 treatment-naïve RCC patients (13%) on sunitinib. Severe hypertension (>200 mmHg systolic or 110 mmHg diastolic) occurred in 32/375 treatment-naïve RCC patients (9%) on sunitinib.

Hypoglycaemia: Sunitinib has been associated with symptomatic hypoglycemia, which may result in loss of consciousness, or require hospitalisation. Hypoglycemia has occurred in clinical trials in 2% of the patients treated with sunitinib for RCC. Reductions in blood glucose levels may be worse in diabetic patients. Check blood glucose levels regularly during and after discontinuation of treatment with sunitinib. Assess if anti-diabetic drug dosage needs to be adjusted to minimise the risk of hypoglycemia.

Infections: Necrotizing fasciitis, including fatal cases, has been reported in patients treated with sunitinib, including of the perineum and secondary to fistula formation. Discontinue sunitinib in patients who develop necrotizing fasciitis.

Myocardial dysfunction/CHF: Patients should be carefully monitored for clinical signs or symptoms of congestive heart failure. Blood pressure should be monitored and managed promptly. In the presence of clinical manifestations of congestive heart failure (CHF), sunitinib should be discontinued. The dose should be interrupted and/or reduced in patients without clinical evidence of CHF but with an ejection fraction $<50\%$ and $>20\%$ below baseline.

Pancreatitis: Pancreatitis was observed in 5 (1%) patients receiving sunitinib for treatment-naïve RCC compared to 1 ($<1\%$) patient receiving IFN- α . If symptoms of pancreatitis are present, patients should discontinue sunitinib.

Proteinuria: Interrupt treatment for 24-hour urine protein ≥ 3 grams and dose reduce. Discontinue for nephrotic syndrome or repeat episodes of protein ≥ 3 grams/24 hours despite dose reductions.

Thyroid Dysfunction: Patients should be observed closely for signs and symptoms of thyroid dysfunction, including hypothyroidism, hyperthyroidism, and thyroiditis, on sunitinib treatment. All patients should have monitoring of thyroid function performed as per Table 1 and be treated as per standard medical practice.

Tumour Lysis Syndrome (TLS): Cases of TLS, some fatal, have been observed in patients treated with sunitinib. Patients generally at risk of TLS are those with high tumour burden prior to treatment. These patients should be monitored closely and treated as clinically indicated.

Thrombotic Microangiopathy (TMA): Thrombotic microangiopathy including thrombotic thrombocytopenic purpura and hemolytic uremic syndrome, sometimes leading to renal failure or a fatal outcome, has been reported in patients treated with sunitinib. Discontinue sunitinib in patients developing TMA. Reversal of the effects of TMA has been observed after treatment was discontinued.

Wound healing: Cases of impaired wound healing have been reported during sunitinib therapy. Temporary interruption of sunitinib therapy is recommended for precautionary reasons in patients undergoing major surgical procedures. There is limited clinical experience regarding the timing of reinitiation of therapy following major surgical intervention. Therefore, the decision to resume sunitinib therapy following a major surgical intervention should be based upon clinical judgment of recovery from surgery.

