6.8.2 Management of sunitinib-related toxicities

Table 11 Dose modifications for sunitinib-related toxicities (including hepatic)

NCI CTCAE toxicity grade	Action
Grade 0, 1, or 2	None
Grade 3^a	Hold sunitinib and follow the algorithm below:

 Toxicity at Grade 3 for ≤7 days and resolves to ≤Grade 1 or baseline Toxicity persists at Grade 3 for >7 days 	
 Resume dosing at one reduced dose level (maximum of 2 dose reductions) Discontinue sunitinib
Grade 4	Follow the algorithm below:

 Expected to be manageable/reversible with dose reduction Not expected to be manageable/reversible with dose reduction 	
 Hold dosing and consult with AstraZeneca study physician Discontinue sunitinib
Recurrence of Grade 3	

 Grade 3 toxicity for ≤7 days and resolves to ≤Grade 1 or baseline Grade 3 toxicity for >7 days 	
 Resume dosing at one reduced dose level (maximum of 2 dose reductions) Discontinue sunitinib
Recurrence of Grade 4	
 Discontinue sunitinib

No more than 2 dose reductions will be allowed for any patient. Patients on 400 mg savolitinib due to weight <50 kg will only be allowed one dose reduction. Patients requiring additional dose modifications due to toxicity will discontinue study treatment.

^a Despite appropriate supportive care

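### Table 11 resumes sunitinib at a reduced dose after any short, resolved Grade 3 toxicity, while Section 6.8.2.1 requires discontinuation for clinical CHF, symptomatic pancreatitis and four other events; no text says which rule prevails

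*Protocol*

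**What the plan says.** Protocol Section 6.8.2, Table 11, sets dose changes for sunitinib by CTCAE grade. Its title covers sunitinib-related toxicities in general and expressly includes hepatic ones. On Grade 3 the drug is held. If the condition "Toxicity at Grade 3 for ≤7 days and resolves to ≤Grade 1 or baseline" is met, the action is "Resume dosing at one reduced dose level (maximum of 2 dose reductions". The row for recurrent Grade 3 repeats that action. The footnote on the Grade 3 row concerns supportive care and exempts no event.

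Section 6.8.2.1, which follows the table, gives actions event by event:

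- Heart failure: "In the presence of clinical manifestations of congestive heart failure (CHF), sunitinib should be discontinued". The next sentence deals with a fall in ejection fraction alone: "The dose should be interrupted and/or reduced in patients without clinical evidence of CHF but with an ejection fraction" below 50% and more than 20% below baseline.
- Pancreatitis: "If symptoms of pancreatitis are present, patients should discontinue sunitinib".
- SJS, TEN or EM: the drug is stopped when signs or symptoms such as "progressive skin rash often with blisters or mucosal lesions) are present, sunitinib should be discontinued". A separate sentence adds "If a diagnosis of SJS or TEN is suspected, sunitinib must not be re-started", which does not name EM.
- Necrotizing fasciitis: "Discontinue sunitinib in patients who develop necrotizing fasciitis".
- TMA and nephrotic syndrome: also discontinue.

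None of these discontinuation rules depends on grade or duration.

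**The concern.** An investigator whose patient has a Grade 3 episode of clinical CHF or symptomatic pancreatitis that settles within a week finds two instructions. The dosing table says hold and then resume at the next lower dose. The event text says stop. A site that works from the table alone would re-expose the patient to a drug that the protocol elsewhere says to discontinue. At stake are patient safety and uniform dosing in the control arm, not the analysis.

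**Working it through.** No figure in the plan is in question, so the check is a comparison of texts.

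**Step 1: do both rules reach the same event?** Table 11 applies to every sunitinib-related toxicity and lists no exception. Section 6.8.2.1 names CHF and pancreatitis as sunitinib risks. Either event, if judged related and Grade 3, falls under both.

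**Step 2: do the instructions differ?**

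| Event: Grade 3, 7 days or less, resolved | Table 11 | Section 6.8.2.1 |
|---|---|---|
| Clinical CHF | Hold, then resume one level lower | Discontinue |
| Symptomatic pancreatitis | Hold, then resume one level lower | Discontinue |
| SJS/TEN/EM, necrotizing fasciitis, TMA, nephrotic syndrome | Hold, then resume one level lower | Discontinue (restart expressly barred for suspected SJS or TEN) |

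The resumed dose comes from Table 8: 50 mg at the start, 37.5 mg at level -1.

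**Step 3: could discontinue mean a temporary hold?** Table 11 uses hold and discontinue as different actions, and discontinuing is its alternative to resuming. Section 6.8.2.1 speaks of interruption when it means a temporary stop. The CHF paragraph is the clearest case, because it keeps interruption or reduction for patients without clinical CHF. Table 11 would give that milder action to patients who have it.

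**Step 4: does any text set an order of precedence?**

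- The fallback in Section 6.8 covers only situations that the guidelines leave out. Here two guidelines apply.
- For savolitinib, Section 6.8.1 sends specific toxicities to their own subsections and leaves Section 6.8.1.3 for the rest. Section 6.8.2 has no such routing for sunitinib.
- Section 3.8 lists adverse events meeting study criteria as a ground for stopping, which leads back to the criteria in conflict.
- The two texts are not cleanly layered as default and exception. Table 11 includes hepatic events by name, yet Section 6.8.2.1 gives a different hepatic rule without the 7-day limit.

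**Step 5: how many patients?** About 50 are to be randomised 1:1, so 50 / 2 = about 25 receive sunitinib. The protocol gives no CHF rate. For pancreatitis it cites 5 cases (1%) in treatment-naïve RCC, without grade or duration. No expected number of affected patients can be derived.

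**The case against.** The strongest reply is that this is an ordinary general rule followed by specific ones. Section 6.8.2.1 is a subsection placed directly after the table, the table never names CHF or pancreatitis, and a reader would normally let the specific rule govern. Timing supports this: Section 6.8.2.1 acts when symptoms appear, whereas resumption comes only after resolution, so a site that follows 6.8.2.1 has already stopped the drug. That is a fair account of the likely intent. It still leaves the site to infer it. At onset a site using the table holds with a path back to treatment, while a site using 6.8.2.1 discontinues.

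It can also be said that only the SJS/TEN text forbids restart, so discontinue may be softer elsewhere. That fails for CHF, where the adjacent sentence separates discontinuation from interruption. It has somewhat more force for pancreatitis, although Table 11's own usage points the other way.

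The practical reach is small, and this stands. Entry requires an ejection fraction of at least 50% and excludes recent NYHA Grade 2 or higher CHF and pancreatic inflammation. ECHO or MUGA is repeated every 12 weeks. After the final analysis, Section 4.3.5 moves sunitinib patients to standard practice and the national label.

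A reader might infer more than the documents support:

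- *That patients will be restarted after CHF.* Nothing shows how often, if ever, any of these events would be Grade 3 and resolve within 7 days.
- *That a definite share of the table or of the named events is in conflict.* Such a count needs CTCAE grading text and resolution times that the protocol does not contain.
- *That the stricter text should always win.* For hepatic events and hypertension, 6.8.2.1 is softer than parts of Table 11, and the protocol does not show that the table should override it there.

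**Conclusion.** The instruction is wrong as written, at low severity: a correction that could be made, not one on which the trial depends. For a Grade 3 toxicity of 7 days or less that resolves to Grade 1 or baseline, Table 11 and Section 6.8.2.1 give incompatible directions for clinical CHF and symptomatic pancreatitis, and the table likewise fails to except the other four events. CHF is the sharpest case. The conclusion rests on the protocol's wording alone. That one of these events would meet the Grade 3 and 7-day condition in practice is an assumption. The sample size and the PFS analysis are untouched.

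**What to change.** Add one footnote to Table 11: *For clinical CHF, symptomatic pancreatitis, signs or symptoms of SJS/TEN/EM, necrotizing fasciitis, TMA and nephrotic syndrome, discontinue sunitinib as per Section 6.8.2.1 regardless of CTCAE grade or duration; do not resume under this table.*

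The footnote should stop there. A general clause giving precedence to the more restrictive action would also settle hepatic and hypertension management against the event-specific text, which is a separate clinical question.

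There is no cost to the design, data collection or analysis. If the sponsor regards the change as substantial, Section 10.5 requires a new protocol version and ethics approval, so it is best carried in the next amendment together with a note to sites that still treat sunitinib patients.

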7. INVESTIGATIONAL PRODUCT AND OTHER TREATMENTS

7.1 Identity of study medications

AstraZeneca will supply savolitinib tablets for oral use. The tablets will be supplied in the 200-mg strength, in open-labelled high-density polyethylene (HDPE) bottles. Additional information about the investigational product may be found in the IB.

Sunitinib will be sourced locally in US and dispensed by the sites. In other countries, Sunitinib will be packed, labelled and distributed by AZ through the IVRS/IWRS.

Sunitinib will be the commercial carton supplied by Pfizer. The original carton will be the labelled with a clinical study label and contain the original blister packs and English language patient information leaflet.

Table 12 IP strength and manufacturer

Investigational product	Dosage form and strength	Manufacturer
Savolitinib	200 mg tablets	AstraZeneca, Sweden
Sunitinib	25 mg & 12.5 mg capsules	Pfizer

7.2 Dose and treatment regimens

7.2.1 Savolitinib

Savolitinib will be dosed as follows:

For patients ≥ 50 kg at the start of treatment, savolitinib 600 mg PO QD, and for patients < 50 kg at the start of treatment, savolitinib 400 mg PO QD will be administered in 42-day (6-week) treatment cycles.

Savolitinib is to be administered with a meal. The time of day for administration of savolitinib should be consistent and the actual time the dose is taken should be recorded in the eDiary each day.

On scheduled PK collection days and clinic visit days the patient should be instructed to wait until he/she arrives at the study centre to take their study medication with a meal when instructed.

If the patient misses a dose of study medication, the patient should take the dose as soon as possible, but not less than 12 hours before the next dose is due.

If vomiting occurs after taking the study medication, the patient should be instructed not to retake the dose. Patients should take the next scheduled dose of savolitinib. If vomiting persists, the patient should contact the investigator. Ondansetron or another serotonin-receptor antagonist may be used.

Patients should be instructed to bring any unused savolitinib in the original bottles, in addition to returning any empty bottles to each clinic visit. Savolitinib dosing compliance/drug diary should be reviewed with the patient at each clinic visit, including the visit at the beginning of each cycle when study medication is dispensed.

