3.6.2 Prohibited concomitant medications and treatments

No other investigational therapy should be given to patients. No anticancer agents should be given to patients other than the study medications. If such agents are required for a patient, then the patient must first be withdrawn from the study.

Herbal preparations/medicines

Herbal preparations/medications are not allowed throughout the study. These herbal medications include, but are not limited to St. John's wort, kava, ephedra (ma huang), ginkgo biloba, dehydroepiandrosterone (DHEA), yohimbe, saw palmetto, and ginseng. Patients should stop using these herbal medications 7 days prior to the date of randomisation (3 weeks for St John's wort).

Statins

For patients on savolitinib, discontinuation of statins is advised unless considered essential, in which case, the patients should be prescribed the lowest available dose and monitored for the effects of increased statin exposure.

Acetaminophen (Paracetamol)

The administration of acetaminophen (paracetamol) is restricted to 3 grams per day, or the maximum dose approved locally (if less than 3 grams per day) during the study. In the event of an elevation in hepatic transaminases or bilirubin, the use of acetaminophen should be avoided until resolution of the affected parameter.

Drugs that prolong QT interval

The concomitant administration of drugs known to prolong QT interval is restricted unless considered essential due to patient management, in which case, patients should be closely monitored with more frequent ECGs. Additional guidance on drugs known to prolong QT interval is provided in Appendix I.

Food restrictions

Patients should abstain from eating grapefruit and Seville oranges (and other products containing these fruits, eg, grapefruit juice or marmalade) during the study.

UV exposure

During savolitinib therapy and for 4 weeks after the last dose, patients should be advised to avoid prolonged exposure to the sun, wear protective clothing, a hat and seek shade from the sun as far as possible; in addition, SPF30+ sunscreen should be used. Exposure to other sources of UV light including sunbeds and tanning booths, etc. should be avoided.

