tilidine
tipranavir
tolvaptan
triazolam
varafenafil
vicriviroc
voclosporin

Savolitinib is a weak competitive inhibitor of CYP2C8 ($IC_{50}=9.1\mu M$). Those drugs defined as potent 2C8 substrates (almost exclusively metabolised by 2C8, such as Repaglinide, Dasabuvir and Rosiglitazone) should be used with caution.

Savolitinib is not a substrate of P-glycoprotein (Pgp) but is a weak inhibitor in vitro ($IC_{50}=17.9\mu M$). Drugs that are known to be affected by Pgp such as digoxin, quinidine, loperamide, saquinavir and ritonavir should be used with caution.

Appendix I Guidance Regarding Potential Interactions of Savolitinib with Concomitant Medications Known to Prolong QT Interval

Drugs that prolong QT interval

The drugs listed in this section are taken from information provided by the Arizona Center for Education and Research on Therapeutics website (available at URL: <https://www.crediblemeds.org>). The website categorizes drugs based on the risk of inducing Torsades de Pointes (TdP).

During screening the drugs that patients are currently prescribed should be checked opposite the ArizonaCert website above.

Drugs with a known risk of Torsades de Pointes

The following drugs prolong the QT interval and are clearly associated with a known risk of TdP, even when taken as recommended (Table I1). These drugs must have been discontinued prior to the start of administration of study treatment in accordance with guidance provided in the table below and should not be co-administered with savolitinib and for a period of one week after discontinuing study treatment. The list of drugs may not be exhaustive and is subject to change as new information becomes available. As such investigators are recommended to search the website to provide the most up to date information.

Table I1 Drugs with known risk of TdP

Drugs with a known risk of TdP	
Drug name	Withdrawal period prior to study treatment start
Anagrelide, ciprofloxacin, clarithromycin, cocaine, droperidol, erythromycin, levofloxacin, ondansetron, papaverine hydrochloride, procainamide, sulpiride, sultopride, terfenadine, terlipressin	2 days
Cilostazol, cisapride, disopyramide, dofetilide, domperidone, flecainide, gatifloxacin, grepafloxacin, ibutilide, moxifloxacin, oxaliplatin, propofol, quinidine, roxithromycin, sevoflurane, sotalol, sparfloxacin, thioridazine	7 days

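### Section 7.2.1 permits ondansetron for persistent vomiting on savolitinib, with no QT condition, although Appendix I says it should not be given with savolitinib

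*Protocol*

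**What the plan says.** Section 7.2.1 (savolitinib dosing) tells a patient whose vomiting persists to contact the investigator, and then states "Ondansetron or another serotonin-receptor antagonist may be used". It attaches no QT, ECG or essential-use condition and does not point to Section 3.6.2 or Appendix I.

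Appendix I covers drugs with a known risk of TdP. The 2-day withdrawal row of Table I1 includes "droperidol, erythromycin, levofloxacin, ondansetron, papaverine hydrochloride". Of the listed drugs the appendix says "These drugs must have been discontinued prior to the start of administration of study treatment", and that they "should not be co-administered with savolitinib and for a period of one week after discontinuing study treatment". It gives no exception. It adds "The list of drugs may not be exhaustive and is subject to change" and sends investigators to a website for current information.

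Section 3.6.2 says "The concomitant administration of drugs known to prolong QT interval is restricted unless considered essential due to patient management". Where that exception is used, it asks for close monitoring with additional ECGs. It then refers to Appendix I for additional guidance.

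Section 7.2.2 repeats the ondansetron sentence for sunitinib.

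**The concern.** One named drug, given with one study drug, is permitted without condition in the dosing section and ruled out in the appendix. An investigator treating persistent vomiting would naturally look in the dosing section, and Section 7 does not lead from there to the QT rules. Section 7.7.2, on concomitant-medication restrictions, points only to Appendix H, and Sections 7.7.1 to 7.7.3 do not mention QT.

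The stake is patient safety. Section 6.8.1.5 lists QTc prolongation as an identified savolitinib risk. The thorough QT study at 600 mg, the trial dose for patients of 50 kg or more, was positive: the upper limits of the two-sided 90% CI for placebo-adjusted change in QTcF were 13.6 and 14.0 msec at 4 and 5 hours. A site relying on Section 7.2.1 alone could start ondansetron with no added ECG.

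**Working it through.** No arithmetic decides this point, so the check is a comparison of the provisions that apply to a savolitinib patient with persistent vomiting.

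| Provision | Rule for ondansetron with savolitinib | Condition |
|---|---|---|
| Section 7.2.1 | Permitted, by name | None |
| Appendix I, Table I1 | Not to be co-administered, nor for one week after stopping; 2-day withdrawal beforehand | No exception |
| Section 3.6.2 | QT-prolonging drugs restricted | Allowed if essential, with more frequent ECGs |
| Exclusion criterion 17 | Patient on a QT/TdP drug (Appendix I) not entered | Applies at entry only |

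1. **Do Section 7.2.1 and Appendix I conflict?** Yes. Both name ondansetron and both concern savolitinib. Permission in one place for what another place rules out is a contradiction.

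2. **Does any text resolve it?** No. No provision exempts ondansetron, and none ranks the dosing section above the appendix. Section 7.2.1 cannot prevail as the more specific text, because Appendix I is equally specific: it lists the drug by name.

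3. **Can Sections 3.6.2 and 7.2.1 be reconciled?** Only if the reader imports the Section 3.6.2 condition into Section 7.2.1. Doing so adds the ECGs but still leaves ondansetron co-administered with savolitinib, contrary to Appendix I.

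4. **Can Section 3.6.2 and Appendix I be reconciled?** Yes. Section 3.6.2 can be read as the general rule for QT-prolonging drugs, with Appendix I as a stricter rule for the known-TdP subset. Ondansetron is in that subset, so this reading places Section 7.2.1 against the stricter rule.

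5. **What would monitoring detect?** Under Table 1, footnote 10, triplicate ECGs are weekly in cycle 1, then once per 6-week (42-day) cycle, at end of treatment, and when clinically indicated. Table 10 acts only once prolongation has been found. After the final analysis, Section 4.3.5 leaves monitoring to the investigator's standard practice.

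**The case against.** The best defence is that the body text already governs. Section 3.6.2 applies whether or not Section 7.2.1 repeats it, and a site that follows it adds ECGs. Section 7.2.1 is permissive, offers an alternative within the class, and routes the patient to the investigator. ECGs are weekly in cycle 1 and available when indicated. All of that stands, and it limits the consequence. It does not remove the contradiction, since a site following both Sections 7.2.1 and 3.6.2 would still breach Appendix I.

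Some broader claims are tempting, but the document does not support them:

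- **That the protocol sets rival QT rules for every Table I1 drug.** Section 3.6.2 and Appendix I can be read as a general rule and a stricter subset. The text should say so, but the two need not be rivals.
- **That Section 7.2.2 is contradicted in the same way.** The Appendix I co-administration bar names savolitinib only. The QT paragraph of Section 3.6.2 is not limited to one arm, unlike the statin paragraph ("For patients on savolitinib, discontinuation of statins is advised unless considered essential"), so it reaches sunitinib patients. At most, Section 7.2.2 lacks a cross-reference.
- **That Section 6.8.1.5 conflicts.** Leaving antiemetic treatment to local practice names no drug and remains subject to Section 3.6.2.
- **That other serotonin-receptor antagonists are barred.** Table I1 names none besides ondansetron. The list is stated to be possibly incomplete, so the document leaves this open.

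**Conclusion.** The point holds as an internal inconsistency between Section 7.2.1 and Appendix I, with Section 3.6.2 adding a condition that Section 7.2.1 omits. It should be fixed: following Section 7.2.1 as written breaks a stated restriction on an identified cardiac risk. Recruitment has closed, but patients may remain on savolitinib for as long as they benefit, so the text still matters.

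The number of patients affected cannot be estimated. A reader might take the causally related vomiting rate in Section 1.1.3.4 (56/233 = 24.0%) and apply it to an assumed 25 savolitinib patients, half of about 50, to get 25 × 0.240 = 6.0. That figure does not measure exposure to the conflict. It counts any causally related vomiting, whereas Section 7.2.1 applies only when vomiting persists. It pools doses from 100 to 1000 mg per day, including 60 patients on 500 mg BID. It also counts the whole arm from the start, although Appendix I entered only with version 4.0 of 26 July 2018. The document gives no frequency of ondansetron use and no QT effect of the combination.

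There is no effect on the efficacy analysis. The conclusion rests only on the current wording of the three provisions.

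**What to change.** 1. **Section 7.2.1:** delete ondansetron. State that any antiemetic given with savolitinib must not be a Table I1 drug and must be checked against the website cited in Appendix I. Cross-refer to Section 3.6.2 and Appendix I.
2. **Section 3.6.2:** add one sentence saying that, for patients on savolitinib, the Appendix I bar governs known-TdP (Table I1) drugs, and the essential-use exception with extra ECGs applies to other QT-prolonging drugs.
3. **Section 7.2.2:** add only a cross-reference to Section 3.6.2.
4. **Sites:** notify those with patients still on treatment.

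The conflict should not be settled by loosening Appendix I to match Section 7.2.1 or the essential-use exception. Nothing in the protocol supports weakening that bar.

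The cost is short edits in three sections and one site letter. No ECGs are required beyond those Section 3.6.2 already asks for, and the analysis does not change. Savolitinib patients lose ondansetron as an option, which Appendix I already intends.
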